10.0 Data

Patient data will be collected from their medical record. Data collected from Epic/patient’s MUSC EMR will be coded in the research database. Data collected include:

1. Demographics: sex, age, race
2. Stroke risk factors: history of HTN, HLD, A-fib, or DM
3. Stroke specifics: type of stroke (hemorrhagic vs ischemic), location of stroke, stroke severity (measured by NIHSS & MRS), time of symptoms to presentation, intervention (tPA or thrombectomy) and complications
4. Physical Performance and Functional Measures: Postural assessment stroke scale scores on evaluation, day three and 30 day follow up. Discharge disposition recommended vs ultimate discharge disposition, hospital length of stay.

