5.0 Study Endpoints

Physical Performance and Functional Measures: PASS scores & AMPAC scores on evaluation, day three, discharge, and 30-day follow up. Discharge disposition recommended vs ultimate discharge disposition, hospital length of stay, and 30-day readmission. The primary outcome is a change in functional mobility measure- the Postural Assessment Scale for Stroke from PT evaluation to discharge from hospital.

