6.0 Setting

This research will be conducted on the inpatient stroke service at MUSC (ED, 9E, 9W, 8W, ICU) as soon as possible after admission, ideally within the first 24 hours of the patient's admission to the vascular neurology service for an acute stroke. Follow up values will be collected at post discharge neurology clinic (either in person or through password protected zoom call, or doxy.me) by a member of the study team. Adverse events will be documented in the patient's medical chart and research record and the primary investigator will direct and oversee services provided.

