12.0 Outcomes and Analysis

Goal enrollment is 168 participants. Based on the past literature, in similar populations the standard deviation of PASS measurements is at the most 7.20.⁵ Using this, with a sample of 42 patients in each group, with 95% confidence at the end of the study we can estimate this difference within a margin of error of 2.8.

The primary outcome measure will be the change in postural assessment stroke scale scores from time of PT evaluation to hospital discharge. A factorial design will allow for a test of intensity (vs control) and duration (vs control) through pooling across treatment arms. Using the table below, margins (A+C, B+D, A+B, C+D) need to each be 104 given a mean difference of 2.8, standard deviation of 7.2, 80% power and 5% type I error. Given that this is an early phase study, we can increase the type I error to 10% which would decrease the overall sample size needed to 168 patients (42 per arm) whilst still maintaining 80% power.

	Low Intensity	High Intensity	Totals
Low Duration	A	B	A+B
High Duration	C	D	C+D
Totals	A+C	B+D	A+B+C+D

We are planning to conduct the analysis using intention to treat paradigm. In a preliminary analysis we will compute all summary statistics. Initial plots, such as spaghetti plots, will be used to guide our analyses. A general linear mixed model approach will be used to analyze all the outcomes. This model will account for the correlations between time points using either a compound symmetric or spatial structure for the covariance matrix. Post-hoc analyses using Tukey type adjustments will be performed to obtain least squares estimates of the differences between the two randomized groups. Although the study is powered based on only the primary

outcome (PASS), we will apply multiple comparisons adjustments for the rest of the outcomes, using Bonferroni corrections. We will test for the assumptions using diagnostic procedures and take appropriate actions if needed. Also, we will define an outcome to be ‘favorable’ or ‘unfavorable’ based on a threshold and apply generalized linear mixed models with logistic link and repeat the analyses. We will attempt to minimize drop-outs but in case of missing data, we will assume Missing at Random or Missing Completely at Random. If necessary, we will perform multiple imputations. For all analyses, we will use SAS, (MIXED, GLIMMIX, MI and MIANALYZE).

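### 30-day readmission is an endpoint, but the plan does not define it, omits it from the data list, and gives no way to find admissions to other hospitals

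*Combined protocol and SAP*

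**What the plan says.** Section 5.0 (Study Endpoints) closes its list of non-primary endpoints with "Discharge disposition recommended vs ultimate discharge disposition, hospital length of stay, and 30-day readmission". It does not say whether readmission is all-cause or stroke-related, whether it means any hospital or only this one, or whether the 30 days run from stroke, admission or discharge.

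Section 10.0 (Data) gives the general source: "Patient data will be collected from their medical record". The next sentence identifies the record: "Data collected from Epic/patient’s MUSC EMR will be coded in the research database". The matching item in that section's list stops one element short of Section 5.0: "Discharge disposition recommended vs ultimate discharge disposition, hospital length of stay". Readmission is not on the list.

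Section 6.0 (Setting) provides a second channel: "Follow up values will be collected at post discharge neurology clinic", in person or by video, by a study team member. Section 9.0 (Study Design) places this contact at 30 days and gives PASS, AMPAC and mRS as the functional measures for it. Neither section mentions asking about admissions.

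Section 12.0 (Outcomes and Analysis) assumes missing data are MAR or MCAR, with multiple imputation if needed. It has no rule specific to readmission.

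**The concern.** An endpoint needs a definition, a source and a rule for patients in whom it was not observed. Readmission has none of these in writing. The one record named belongs to a single hospital. Unless outside admissions reach that record, which the documents do not say, a patient admitted elsewhere looks the same in the chart as a patient never readmitted. Someone abstracting a yes/no field from that chart could easily enter 'no' for both.

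That error would be misclassification, not missingness, so the imputation provision in Section 12.0 would not act on it. It has to be prevented when the data are collected.

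Two features of the trial make equal capture across arms uncertain. Length of stay is an outcome that the interventions are expected to change (Section 1.0), and discharge disposition is itself an endpoint. Either could affect where a patient is later admitted, and how much time after discharge the 30-day contact covers.

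**Working it through.** **No stated figure to reproduce.** The documents give no readmission rate, no share of admissions elsewhere and no power for this endpoint. The only sample-size calculation is for PASS, and this point does not touch it. That calculation does reproduce. With n = 2(z₁₋α/₂ + z₀.₈₀)² × 7.2²/2.8², n is 104 per margin at two-sided 5% (stated 104) and 82 at 10% (planned 84, where power is 80.9%).

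**What each section supplies for readmission**

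| Section | Definition | Source | Coding if not observed |
|---|---|---|---|
| 5.0 Study Endpoints | name only | none | none |
| 6.0 Setting | none | 30-day contact exists, not assigned to it | none |
| 9.0 Study Design | none | same contact; functional measures named | none |
| 10.0 Data | not listed | trial hospital's record, in general terms | none |
| 12.0 Outcomes and Analysis | none | none | general MAR/MCAR only |

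**Illustration of size.** The only input from the documents is 84 patients per factorial margin (2 × 42). All rates and capture shares below are assumptions. Let p be the true rate and s the share of readmissions captured, with no false positives, so the recorded rate is p × s.

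*Equal capture, effect on the rate.* Assume p = 12% and 10-30% of events missed.
- 0.12 × 0.90 = 10.8%; 0.12 × 0.70 = 8.4%.
- In patients: 84 × 0.12 ≈ 10 events per margin, of which about 1 (10%) to 3 (30%) are missed.

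*Equal capture, effect on the comparison.* Assume true rates of 15% and 7.5%. Power is Φ[(|p₁ − p₂| − 1.645 × SE₀)/SE₁], with SE₀ pooled, SE₁ unpooled, 84 per margin and two-sided 10%.

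| Captured | Recorded rates | Risk difference | Risk ratio | Power |
|---|---|---|---|---|
| 100% | 15.0 vs 7.5% | 7.5 points | 2.0 | 46% |
| 90% | 13.5 vs 6.75% | 6.75 | 2.0 | 42% |
| 80% | 12.0 vs 6.0% | 6.0 | 2.0 | 39% |
| 70% | 10.5 vs 5.25% | 5.25 | 2.0 | 35% |
| 50% | 7.5 vs 3.75% | 3.75 | 2.0 | 28% |

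From full to 50% capture, power falls from 34% to 21% for true rates of 10% vs 5%, and from 57% to 34% for 20% vs 10%. These powers are before the Bonferroni correction that Section 12.0 plans for outcomes other than PASS, so they are upper figures. Power is low even with complete capture.

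*Unequal capture, no true difference.* Assume p = 12% in both groups, with 90% captured in one and 70% in the other.
- False difference: 0.12 × (0.90 − 0.70) = 2.4 points; risk ratio 0.90/0.70 = 1.29.
- SE with 84 vs 84: √(2 × 0.12 × 0.88/84) = 5.0 points.
- Ratio: 2.4/5.0 ≈ 0.5 SE.
- For p from 10% to 20%, the false difference is 2 to 4 points.

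**Clock start.** Section 1.0 refers to 30 days post stroke for mRS, and Section 9.0 ends study procedures after the 30-day appointment. If that appointment is timed from the stroke, a patient discharged on day L has been observed for only 30 − L days after discharge. Section 3.0 reports a stay 1.5 days shorter in the Phase I treatment arm. A difference of that size would give the arms post-discharge windows differing by 1.5 days on average.

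**The case against.** The strongest reply is that this is loose drafting on a minor endpoint. Most of its parts are fair.

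- **The hospital record is not the only stated source.** A reader might infer that it is, but Sections 6.0 and 9.0 provide direct 30-day contact at which admissions could be asked about. What stands is that the plan does not say they will be.
- **No coding rule is stated.** A reader might infer that a patient admitted elsewhere is scored as not readmitted, or that a death after discharge counts as a good outcome. The documents say neither. Recording an outside admission as 'no' is a risk of the plan as written, not a documented rule.
- **The Section 10.0 list is not exhaustive.** It is introduced as a list of what the data include. It omits AMPAC and the discharge PASS, and it contains the 30-day PASS, which comes from the follow-up contact. So the omission of readmission does not show a decision to rely on the local chart. It also does not supply a source.
- **Under-capture need not shrink every arm difference.** With equal capture the risk ratio is unchanged and only the absolute difference falls. With unequal capture the difference can shrink, grow or reverse.
- **Importance is limited.** Readmission appears in no aim or hypothesis by name, and the study is powered on PASS alone. Safety oversight does not rest on it: adverse events are documented in the chart and research record (Section 6.0), and the investigators meet every 25 patients (Section 11.0).

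None of this provides a definition, a means of finding admissions elsewhere, or a rule for patients who are not reached.

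**Conclusion.** The concern holds as a gap in specification and ascertainment. Readmission is listed but undefined and absent from the data list. The only record named is the trial hospital's own, and the planned 30-day contact is not assigned to capture the event. Followed as written, the plan can miss admissions to other hospitals and record them as no readmission, an error that the missing-data methods would not correct.

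The size is unknown. Under the assumed capture shares the effect is modest: one to three events per margin at a true 12%, and a spurious difference of about half a standard error under a marked imbalance in capture. Whether capture would differ by arm cannot be determined from the documents, which do not say where patients go after discharge or whether outside admissions reach the record. The primary PASS outcome runs from PT evaluation to discharge and is unaffected. The case for changing the plan rests mainly on how little the change costs.

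**What to change.** 1. **Define the endpoint in Section 5.0:** admission to any hospital within 30 days, with a stated clock start and whether all causes count. Check that the 30-day contact falls at or after the end of that window. If it does not, say how the remaining days are covered.
2. **Add readmission to the Section 10.0 list**, with its sources.
3. **Ask at the existing 30-day clinic or video contact** whether the patient has been admitted to any hospital, with date and hospital. Take the answer from the patient or a proxy and check it against the record.
4. **State the coding rule:** a patient with no contact and no recorded event is missing, not 'no'. The missing-data provisions in Section 12.0 can then apply.
5. **Report deaths separately by arm.** A readmission-or-death composite would change the endpoint and is not needed to repair ascertainment.

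The cost is one question on a form at a contact already planned, plus a few lines of text. The reported rate may be slightly higher, and some values that would have been entered as 'no' will be missing.

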1.0 Objectives and Specific Aims

Goal: *To evaluate the impact of increased frequency and intensity of Physical Therapy (PT) services on patient outcomes in the acute stroke population.*

Aim I: To determine whether increasing the frequency of Physical Therapy services post-acute stroke is superior to standard of care physical therapy services; measured by a change in functional outcomes, hospital length of stay, 30 day follow up.

Hypothesis I: We hypothesize that patients receiving an increased frequency of PT services will demonstrate higher degree of improvement on the Activity Measure for Post-Acute Care (AMPAC) and Postural Assessment Stroke Scale (PASS) from admission to time of discharge from the hospital and at 30-day follow up. We also expect lower overall Modified Rankin Scale (mRS) scores for the increased frequency PT group compared the usual care PT group at 30 days post stroke.

Aim II: To determine whether increasing the intensity of Physical Therapy services post-acute stroke is superior to standard of care physical therapy services; measured by a change in functional outcomes, hospital length of stay, 30 day follow up.

Hypothesis II: We hypothesize that patients receiving an increased intensity of PT services will demonstrate higher degree of improvement on the AMPAC and PASS from admission to time of discharge from the hospital and at 30-day follow up. We also expect lower overall mRS scores for the increased frequency PT group compared the usual care PT group at 30 days post stroke.

Aim III: To determine whether increasing the intensity of Physical Therapy (PT) services post-acute stroke is superior to increasing the frequency of PT services; measured by a change in functional outcomes, hospital length of stay, 30 day follow up.

Hypothesis III: We hypothesize that patients receiving an increased intensity of PT services will demonstrate higher degree of improvement on the AMPAC and PASS from admission to time of discharge from the hospital and at 30-day follow up. We also expect lower overall mRS scores for the increased intensity PT group compared the increased frequency PT group at 30 days post stroke.

Aim IV: To determine whether increasing the intensity and frequency of PT services post-acute stroke is superior to increasing only the intensity of PT services; measured by a change in functional outcomes, hospital length of stay, 30 day follow up.

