Rather than decreasing the time to upright mobility, it may be beneficial to examine the effect of short sessions of more frequent challenging mobilization in these patients, within the early stages of their hospitalization. If, as assumed, a prolonged duration of upright sitting posture has a negative effect on cerebral blood flow¹² it may be possible to gain the positive effects of early mobility by continuing to provide PT services while combating the negative effects of cerebral perfusion by returning all patients to a <30-degree position in bed following therapy services within the first 24 hours of acute stroke admission. This study aims to examine the approach of increased frequency and intensity of physical therapy services as a way to gain the benefits of the publicized early mobility approach, while weighing the concerns raised by previous trials and decreasing amount of time left upright to combat negative effects of cerebral perfusion on the ischemic penumbra. A study similar to our Phase I approach, performed in Taiwan in 2021, demonstrated that survivors of acute stroke who receive up to 2 rehabilitation sessions per day for 5 d/wk. early in their hospitalization have better functional recovery at 3 months after stroke.¹³ Phase I of "Impact of Intense Physical Therapy on Functional Mobility Outcomes in the Acute Stroke Population" demonstrated a significant improvement in functional mobility scores for acute stroke patients mobilized early, frequently and intensely compared to their counterparts in the standard of care arm of the study. The treatment arm progressed on the Postural Assessment Scale for Stroke (PASS) and the Activity Measure for Post-Acute Care (AMPAC). The PASS improved in the experimental group from admission to discharge 6.28 points while the standard of care change was 1.82 points; there was a main effect for interaction ($p=0.0001$). The AMPAC improved in the experimental group from admission to discharge 3.13 points while the standard of care change was 1.48 points; there was a main effect for interaction ($p=0.01$). PASS and AMPAC scores were maintained in both groups at 90 days post-stroke. The level of disability measured by the Modified Rankin Score (mRS) decreased for both groups at 90 day follow up and the length of hospital stay was decreased by 1.5 days in the treatment arm. There was one significant adverse event in the experimental group during the first 30 days post-stroke- due to significant atherosclerosis and perfusion dependence. This patient was removed from the study secondary to having a carotid stent placed. Because of this adverse event, patients who

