7.0 Enrollment

Goal enrollment is 168 participants.

Potential subjects will be identified via chart review on admission to the stroke service and appropriateness of enrollment will be decided by PI based on discussion with the patient's clinical care team. The patient will then be approached on the inpatient stroke service, provided information about the study by a study team member at bedside and have time to ask questions before consent is obtained by a study team member. The PI/study team will already be part of these patients' clinical care and the PT or nurse practitioner obtaining consent will be an approved member of the study team on the eIRB application.

Inclusion/exclusion criteria will be determined based on patient chart review in Epic, once PT consults are received (consults are automatically triggered on admission to the acute stroke service). Thorough chart review and discussion with patient's medical team will serve as a means of determining patient eligibility. Both treatments as usual and experimental group patients will meet the same eligibility criteria and will be randomized to their treatment after consent is obtained.

Inclusion Criteria:

Acute stroke

NIH Stroke Scale score of 2-18 with motor involvement

Age 18-80yo

Medical stability for increased therapy services, determined by Stroke Service NP (no significant uncontrolled fluctuation in vital signs, blood pressures or seizure like activity).

Ability to give informed consent

Oriented x 4 and able to follow commands

Exclusion Criteria:

Medical instability or cerebral perfusion dependence, requiring bed rest

Pregnancy (noted in chart)

Inmates (noted in chart or visible by guards present at bedside)

Known & Current COVID-19 infection (PCR positive labs)

Dialysis (noted in chart & performed while inpatient)

External Carotid Stenting Procedure

Hemorrhagic Stroke

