9.0 Study Design

This study will be designed as a randomized control trial with a 1:1:1:1 randomization. This study will utilize a stratified block randomization design and stratifying on the 4 NIHSS categories to randomly allocate a participate to a treatment group, while maintaining a balance across treatment groups. All patients will be identified and consented as soon as possible, ideally within 24 hours of admission to the stroke service. Patient's blood pressures will be obtained prior to PT treatment to ensure safety of mobilization. If systolic blood pressure is above 220mmHG, therapy services will not be performed at that time and therapist will follow up later in the day once patient is medicated for hypertension by nursing staff.

If a patient is randomized to the frequent physical therapy treatment group, they will receive PT services 2x/day for 3 out of the first 5 days of hospital admission and daily for the remainder of their hospitalization. Sessions will be 20-50 minutes in duration, based on patient tolerance. These PT sessions will include working on getting out of bed, transferring from bed to a chair, working on balance, strengthening the side of the body affected by the stroke, learning how to walk again and/or how to use a wheelchair if unable to walk.

If a patient is randomized to the intense physical therapy treatment group, they will receive PT services daily with treatment sessions being more difficult than a standard therapy session. During each PT session, the things that are difficult for the patient will be made even more difficult (by adding resistance or other challenges) in order to increase the intensity of the session. This is known as "Error Augmentation training" and will be implemented to target at least 3 post stroke deficits identified on evaluation.

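### Hospital length of stay has no stated start time, and its analysis does not adjust for the time between admission and randomisation; this causes no bias but can cost some precision.

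*Combined protocol and SAP*

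**What the plan says.** All four aims in Section 1.0 are "measured by a change in functional outcomes, hospital length of stay, 30 day follow up". Section 5.0 lists "hospital length of stay, and 30-day readmission" among the endpoints, and Section 10.0 lists "Discharge disposition recommended vs ultimate discharge disposition, hospital length of stay" among the data to be collected. None of these places says when the stay starts or ends.

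On timing, Section 9.0 says "All patients will be identified and consented as soon as possible, ideally within 24 hours of admission to the stroke service", and Section 6.0 places the research "ideally within the first 24 hours of the patient's admission to the vascular neurology service for an acute stroke". Section 7.0 says that patients "will be randomized to their treatment after consent is obtained". No eligibility criterion limits the delay from admission to randomisation.

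Section 12.0 applies a general linear mixed model to all outcomes, with Bonferroni correction for those other than the primary. The primary outcome is change in PASS from PT evaluation to discharge. Section 12.0 names no covariate for length of stay. The only figure the document gives for this outcome is from Phase I, in Section 3.0: "the length of hospital stay was decreased by 1.5 days in the treatment arm". It gives no SD.

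**The concern.** An outcome named in four aims should have a defined clock. If stay is counted from hospital admission, each value is the sum of two parts: time before randomisation, which allocation cannot change, and time after it, which it can. The first part differs between arms only by chance, so it leaves the expected difference in mean days alone. It can still add to the variance, more so if patients who consent late also tend to stay longer afterwards.

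Some delay is foreseeable from the plan itself. Section 7.0 requires medical stability, full orientation and ability to consent, and Section 6.0 includes ICU patients. The 24-hour target also runs from admission to the stroke service, whereas the outcome is hospital stay, so the target does not fully bound the pre-randomisation part.

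At stake is the precision of a non-primary, unpowered outcome that must also pass a Bonferroni threshold.

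**Working it through.** **The plan's own calculation.** Section 12.0 uses a PASS difference of 2.8, SD 7.2 and 80% power. With n per margin = 2 × [7.2 × (z_alpha + 0.842) / 2.8]², two-sided 5% gives 104, as stated. Two-sided 10% gives 82, or 164 in total against the stated 168. With 84 per margin, power is 80.9%. The document does not state sidedness; two-sided reproduces its figures. Nothing below affects this calculation.

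**Inputs for length of stay.**
- Difference of 1.5 days (Section 3.0, Phase I).
- 84 against 84 (Section 12.0, pooled margins of 2 × 42).
- Two-sided 10% alpha (Section 12.0), before Bonferroni, because the number of outcomes to be corrected for is not stated.
- Assumed: SD of post-randomisation stay 4 days, with 3 and 6 as a range.
- Assumed: pre-randomisation time uniform over 0 to 24 hours (the target met), SD = 1/√12 = 0.289 day; or uniform over 0 to 3 days (the target missed by some), SD = 3/√12 = 0.866 day.
- Assumed: correlation r between pre- and post-randomisation time of −0.3, 0 or 0.3.

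**Formulas.**
- Whole stay, unadjusted: SD = √(post² + pre² + 2 × r × post × pre).
- Adjusted for pre-randomisation time under a linear model: SD = post × √(1 − r²).
- SE = SD × √(2/84) = SD × 0.1543.
- Power = Φ(1.5/SE − 1.645).

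**Example: 0 to 3 days, r = 0.3.** Whole-stay variance is 16 + 0.75 + 2 × 0.3 × 4 × 0.866 = 18.83, so SD is 4.339, SE is 0.670 and power is 72.4%. Adjusted SD is 4 × √0.91 = 3.816, SE is 0.589 and power is 81.7%.

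**Results, post-randomisation SD 4 days.**

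| Pre-randomisation time | r | Whole-stay SD | Power, whole stay unadjusted | Power, adjusted |
|---|---|---|---|---|
| 0–24 h | 0 | 4.010 | 78.2% | 78.4% |
| 0–24 h | 0.3 | 4.096 | 76.7% | 81.7% |
| 0–24 h | −0.3 | 3.923 | 79.8% | 81.7% |
| 0–3 days | 0 | 4.093 | 76.7% | 78.4% |
| 0–3 days | 0.3 | 4.339 | 72.4% | 81.7% |
| 0–3 days | −0.3 | 3.830 | 81.4% | 81.7% |

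Counting from randomisation without a covariate gives SD 4 and 78.4% throughout. Where r is not zero, the rise from 78.4% to 81.7% comes from the covariate predicting later stay; the rest of the gap is the effect of the pre-randomisation time itself.

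**Other SDs.** For 0 to 24 hours with r = 0, whole stay against adjusted is 94.3% against 94.5% at SD 3, and 48.9% against 49.0% at SD 6. For 0 to 3 days with r = 0.3, it is 89.4% against 96.0%, and 45.8% against 52.1%.

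**Choice of clock.** Whole stay equals post-randomisation stay plus the covariate. In a linear model that contains the covariate, moving from one outcome to the other shifts the covariate's coefficient by exactly 1. The arm estimate and its standard error do not change.

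**The case against.** The strongest reply is that the plan already keeps this interval short. Consent is aimed at 24 hours. The two frequency arms also receive PT "2x/day for 3 out of the first 5 days of hospital admission", which is hard to deliver unless randomisation happens by about hospital day 3. Allocation is unknown beforehand, so that practical limit bears on every participant. If the 24-hour target is met and the delay is unrelated to later stay, the loss is 0.2 percentage points. Length of stay is neither primary nor powered, and total stay is the measure that compares directly with Phase I. All of this stands, and it sets the size of the point.

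It also rules out several stronger readings that a reader might infer:

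- That the plan defines the outcome as the whole stay. It does not define the clock at all; admission to discharge is the natural reading, but an inferred one.
- That several days of untreatable stay seriously weaken the comparison. A pre-randomisation SD of 2 days would cut unadjusted power to 70.2% against 78.4% (r = 0). But an SD of 2 needs a range of at least 4 days, which fits poorly with Section 9.0.
- That pre-randomisation time can only add noise. If late consent leaves fewer days to discharge, whole stay can vary less than post-randomisation stay: 3.830 against 4 days in the table.
- That the clock must be moved to randomisation. With the covariate in the model, the clock makes no difference to the arm comparison.

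What the reply does not remove is that the start time is unstated, the interval is uncapped and no adjustment is planned.

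**Conclusion.** The point holds as a minor one. Length of stay needs a stated clock, and its model should adjust for time from hospital admission to randomisation. There is no bias, because that interval is fixed before allocation and balanced in expectation. The primary outcome and the sample size are untouched.

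The cost of leaving the plan as it is ranges from about 0.2 percentage points of power (target met, no correlation) to about 9 (0 to 3 days, correlation 0.3). At correlation −0.3 over 0 to 3 days, the two analyses are nearly equal, at about 81% and 82%. These figures rest on an assumed SD of 4 days and assumed delays and correlations, since the document gives none. They use a normal approximation and precede any Bonferroni correction. Under a linear model, the adjusted analysis does at least as well as either unadjusted clock, apart from one degree of freedom.

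**What to change.** In Sections 5.0 and 12.0, state that length of stay runs from hospital admission to hospital discharge. In Section 12.0, include time from hospital admission to randomisation as a covariate in the length-of-stay model. Measure it from hospital admission rather than stroke-service admission, so that it matches the outcome.

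Counting from randomisation with the same covariate gives the same arm estimate and standard error, so changing the clock is optional. Keeping total stay preserves comparability with Phase I.

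The cost is a few lines of text and one degree of freedom. The admission and discharge times are in the medical record and the randomisation time is known to the study team. No visit, assessment or change in sample size is needed.
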